## PROTOCOL TITLE: Videoconferencing for Remote Assessment of Physical Performance

**NOTE:** The study described in this protocol is one of two studies proposed in the NCI Cancer Prevention, Control, Behavioral Sciences, and Population Sciences Career Development Award (K07). The K07 is a five-year award. A separate protocol has been submitted for the second study, which is a distance-based light-intensity physical activity intervention for older cancer survivors.

### 1.0 Objectives

#### .1 Primary Objectives and Hypotheses

- 1.1.a The primary objective is to evaluate the validity and reliability of using videoconferencing to assess physical performance tests self-administered by older cancer survivors in their own homes. This remote assessment will be compared to the traditional face-to-face (i.e., in-person) assessment and to accelerometer (activPAL) data.
- 1.1.b We hypothesize that older cancer survivors, in the presence of a family member or friend, will be able to successfully complete the physical performance self-assessment in the home environment.
- 1.1.c We further hypothesize that the results (time to complete performance tests in seconds) between the videoconferencing method and the traditional face-to-face method will be within a clinically acceptable limit (intra-class correlation coefficient (ICC)  $\geq .80$ ).

The ultimate goal of this research study is to develop a test protocol to allow older cancer survivors to self-administer physical performance tests in their own home, while an investigator remotely assesses the tests via videoconferencing. The test protocol includes written and video instructions and the test kit (tablet, tablet stand, measurement tools). To achieve this objective, we will proceed with a series of phases. We will apply a similar concept of “saturation” as is done in qualitative studies. In qualitative studies, the number of focus groups or interviews is based on the saturation point, i.e., the point at which no new information is learned. For the current study, we propose to include a range of participants at each study phase. At the point at which no new information is being learned, i.e., no further adjustments are needed to the test protocol, we will proceed to the next phase.\*\*

Phase 1: First, we will test proof-of-concept that participants will be able to follow the testing protocol and use the tablet PC to communicate with the investigator (10-12 participants). The test protocol will be refined based on what is learned after a minimum of 10 participants. We anticipate no more than 12 participants needed for this phase.

Phase 2: Next, 10-20 new participants will be enrolled to evaluate the validity of videoconference vs. face-to-face assessment (i.e., direct observation) of physical performance. Communication will occur between the remote assessor and the participant. The direct observer will not communicate directly to the participant, unless there is a safety issue. After completing 10 participants without a major change in the test protocol, we will proceed to the next phase.

Phase 3: This phase involves participants repeating the test protocol, but without the face-to-face assessment (i.e., direct observation). This will test the ability of the participant to receive the box of test instructions and materials in the mail or delivered by a study team member, unpack the box, communicate with the remote assessor via videoconferencing, pack up the box, and return it to the study team (postage paid) or retrieved by a study team member. This step will involve 5-10 participants from Phases 1 and 2, who have provided

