A friend, neighbor or relative is requested to be present during the assessment. This person will be able to communicate via the videoconferencing session with the investigator and must have access to a telephone should medical attention be required. However, if this person is unable to be present during the assessment once it has been scheduled, then the research investigator conducting the face-to-face assessment will cover their responsibilities. Face-to-face assessment is the traditional method for assessing these physical performance tests. We will be testing whether the remote assessment via videoconferencing can produce similar results (time in seconds to complete the tests) as the traditional (face-to-face) method.

The two different assessment methods (remote vs. face-to-face) should be within a reasonable margin of error ( $r \geq .80$ ) The two performance tests include the Timed Up & Go (TUG) Test and the 30-second chair stand test (30s-CST). The TUG test involves standing up from a standard

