## 8.0 Study Endpoints

### 8.1 Primary and secondary study endpoints

8.1.a. Proof-of-concept that participants will be able to follow the testing protocol and use the tablet to communicate with the investigator. We will track technology issues (use of tablet, cellular reception, audio and video quality) as well as non-technology issues (understanding of test instructions, safety issues).

8.1.b Evaluation of the validity and reliability of videoconference vs. face-to-face assessment of physical performance. Both performance tests are timed tests (time in seconds to complete the TUG test; number of stands in 30 seconds). The validity

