## PROTOCOL TITLE: Videoconferencing for Remote Assessment of Physical Performance

of the videoconference assessment will be evaluated using the limits of agreement statistic, which is the range within which 95% of differences between measurements obtained by 2 methods will lie. The videoconference assessment will be considered valid if the limits of agreement are within a clinically acceptable limit. This limit will be determined *a priori* through discussions between the PI and her mentoring team after the proof-of-concept portion of the study (first 10 participants). This will provide a better idea of inter-rater differences in timing these tests, under ideal conditions (both investigators directly observing the tests at the same time). The clinically acceptable limit will need to take inter-rater difference into account, i.e., a limit that is at or above the inter-rater difference under ideal conditions. Intraclass Correlation Coefficients (ICC) will be used to examine intra-rater and inter-rater reliability of the videoconference assessment of physical performance. Interpretation of ICC values is as follows: 0.75-1.00 = excellent reliability; 0.60-0.74 = good reliability; 0.40-0.59 = fair reliability; and <0.40 = poor reliability.

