## PROTOCOL TITLE: Videoconferencing for Remote Assessment of Physical Performance

instructions, starts, stops, and times test using a standard stopwatch). The other investigator will be at the participant's home to observe and time the tests. The videoconferencing software records the assessments for later viewing and scoring (i.e., timing via stopwatch). One-month later, the investigator who performed the videoconferencing assessment will watch the video recording and re-score the tests to determine intra-rater reliability. At least 3 different investigators will watch the video recordings and score the tests (using a stopwatch) to determine inter-rater reliability. All investigators will receive specific training in how to time the performance tests.

For Phase 3, individuals who provided consent to re-contact will be invited to repeat the study, only this time, without a direct observer in their home. Since these participants will have already completed the study, we anticipate the test instructions should be sufficient for the participants to safely self-administer the two physical performance tests in their own home, while only communicating with the remote assessor (located at UNM). Otherwise, further improvements/clarifications to the test instructions will be made.

For Phase 4, newly enrolled participants will complete the study as in Phase 3. Phase 4 eliminates the practice effect among the participants repeating the study in Phase 3.

\*\*A copy of the video instructions for the study participant has been uploaded as a supporting document. The video is also available on YouTube via this private link: <https://youtu.be/k5bHRnjNcuo>.

Participants will wear an activity monitor during their physical performance test. The ActivPAL3 activity monitor is a small device (2.4 x 4.3 x 0.5 cm; 10g) that will be attached to the anterior midline of the thigh using a PALStickie™ (a double-sided hypoallergenic sticky pad) or Tegaderm Dressing (a transparent dressing/tape). The ActivPAL3 provides time-stamped data (sitting, standing, and stepping) that will be used to further assess the validity and reliability of the videoconferencing method to assess physical performance.

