### *Analyses*

The validity of the videoconference assessment will be evaluated using the limits of agreement statistic, which is the range within which 95% of differences between measurements obtained by 2 methods will lie. The videoconference assessment will be considered valid if the limits of agreement are within a clinically acceptable limit. This limit will be determined *a priori* through discussions between the PI and her mentoring team. Intraclass Correlation Coefficients (ICC) will be used to examine intra-rater and inter-rater reliability of the videoconference assessment of physical performance. Interpretation of ICC values is as follows: 0.75-1.00 = excellent reliability; 0.60-0.74 = good reliability; 0.40-0.59 = fair reliability; and <0.40 = poor reliability.

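### The primary hypothesis judges remote versus face-to-face agreement by ICC ≥ .80 (r ≥ .80 in the Background), but the validity rule uses limits of agreement, and the two can give opposite answers

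*Combined protocol and SAP*

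**What the plan says.** Three statements cover the same comparison, remote against face-to-face.

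- **Section 1.1.c** hypothesizes that results "between the videoconferencing method and the traditional face-to-face method will be within a clinically acceptable limit (intra-class correlation coefficient (ICC" ≥ .80.
- **Section 2.0 Background:** "The two different assessment methods (remote vs. face-to-face) should be within a reasonable margin of error", with r ≥ .80 given as that margin.
- **Sections 8.1.b and 10.0 (Analyses):** "The videoconference assessment will be considered valid if the limits of agreement are within a clinically acceptable limit". The limit is to be agreed between the PI and mentors. Section 8.1.b places this after the proof-of-concept participants and says the limit may not be smaller than the difference between two raters who both watch directly. It is therefore a quantity in seconds or stands.

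The ICC has another role in the analysis text. In section 10.0, ICCs "will be used to examine intra-rater and inter-rater reliability of the videoconference assessment of physical performance". Section 9.0 ties that work to the recordings: the remote assessor re-scores after a month, and "At least 3 different investigators will watch the video recordings and score the tests (using a stopwatch) to determine inter-rater reliability". The scale for reading ICCs is "Interpretation of ICC values is as follows: 0.75-1.00 = excellent reliability", with lower bands below that.

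The outcomes are "time in seconds to complete the TUG test; number of stands in 30 seconds". Of the Phase 2 sample, section 1.0 says "10-20 new participants will be enrolled to evaluate the validity of videoconference vs. face-to-face assessment".

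**The concern.** Section 1.1.c and the validity rule use the same expression for the acceptable limit but mean different things: a fixed, unit-free .80 in one, and a bound on the measurement scale in the other. No section ranks the criteria or says what is concluded if they disagree.

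ICC and r depend on how much participants differ from one another and set no bound in seconds or stands. In addition, r ignores a constant offset between methods. A varied sample can reach .80 with differences too wide to accept, and a homogeneous sample can miss .80 although the two methods agree closely.

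Validity and reliability are the primary objective in 1.1.a. A report could say that 1.1.c was met, in words that sound like clinical acceptability, while the limits of agreement fail. It could also say 1.1.c was not met when they pass.

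**Working it through.** The documents give no SD, no numerical limit and no power calculation, so there is no figure of the plan's own to reproduce. The check expresses everything in units of T, the total observed SD, taken as equal in both methods.

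**1. What ICC .80 means as limits of agreement, without bias.** The SD of the difference is T√(2(1 − ICC)), so the half-width is 1.96 × √(2(1 − ICC)) × T. At ICC .80 this is 1.96 × √0.40 × T = 1.24 T. For assumed TUG SDs of 1, 2, 3 and 5 s that is ±1.24, 2.48, 3.72 and 6.20 s, so ICC .80 fixes no limit in seconds.

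**2. The ICC that the limits-of-agreement rule requires.** For an acceptable limit L, the ICC needed is 1 − (L/(1.96 T))²/2.

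| Limit L | ICC needed | Consequence |
|---|---|---|
| 0.5 T | .967 | ICC from .80 to .967 meets 1.1.c, fails the rule |
| 0.75 T | .927 | same, .80 to .927 |
| 1.0 T | .870 | same, .80 to .870 |
| 1.24 T | .800 | criteria coincide |
| 1.5 T | .707 | ICC from .707 to .80 passes the rule, fails 1.1.c |
| 2.0 T | .479 | same, .479 to .80 |

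**3. A constant bias.** Take a bias of 0.5 T (illustrative) with r = .80. The values of r and of a consistency ICC stay at .80. The absolute-agreement ICC is .80/(1 + 0.5²/2) = .80/1.125 = .711. The limits become 0.5 T ∓ 1.24 T, that is −0.74 T and +1.74 T. So the form of the ICC, which the plan does not state, can itself change the verdict.

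A second illustration assumes SD 3 s, error SD 0.2 s and bias 2 s. Then r = .996 and the absolute-agreement ICC = .815, so both pass. The limits are 1.45 to 2.55 s, which fails any limit below 2.55 s.

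**4. Simulated verdicts at the Phase 2 sample sizes.** Each setting used 4,000 studies without bias, comparing an absolute-agreement ICC estimate ≥ .80 with estimated limits inside ±L. All SDs, ICCs and limits are assumptions.

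| Assumed setting | True half-width | ICC passes, limits fail (n=10 / n=20) | Limits pass, ICC fails (n=10 / n=20) |
|---|---|---|---|
| SD 3 s, ICC .92, L 2 s | 2.35 s | 76.7% / 89.2% | 0% / 0% |
| SD 3 s, ICC .92, L 3 s | 2.35 s | 18.3% / 12.7% | 2.7% / 0.8% |
| SD 1 s, ICC .75, L 2 s | 1.39 s | 0.2% / 0% | 57.5% / 69.7% |

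Disagreement can be common in either direction or fairly uncommon, depending on values the documents do not contain.

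**5. Precision.** The 95% CI half-width of one limit is t(n−1) × √(1/n + 1.96²/(2(n−1))) SDs of the difference: 1.27 at n = 10 and 0.81 at n = 20. For an observed consistency ICC of .80, F = 1.8/0.2 = 9 and the F-based 95% CI is .38 to .95 (n = 10) or .56 to .92 (n = 20).

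**The case against.** The best defence is that the plan has only one decision rule. Only 8.1.b and 10.0 say when the method counts as valid, and both name limits of agreement. Section 1.1.c states an expectation and 2.0 is narrative. On this reading, a high ICC with wide limits is simply a pair of results to report. It is true that limits of agreement are the deciding rule. But 1.1.c is the stated primary hypothesis, it concerns the same between-method comparison, and it describes the result in the same terms as the validity rule.

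A between-method ICC may also be intended. The two methods are scored by two investigators at once, and 8.1.b and 9.0 pair validity and reliability of videoconference against face-to-face. That is a fair reading, but no section plans this ICC, gives its form or tests it against .80. The interpretation bands do not supply the threshold either: an ICC of .75 to .79 would be excellent there and fail 1.1.c. That bands need not match a hypothesis threshold is conceded.

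Two points stand. The 0.5 T bias and the simulated percentages are illustrations, not forecasts for this study. And the limits-of-agreement rule has no number in the documents, while Phase 2 was already under way when the pandemic stopped home visits (section 9.0), so moving weight onto an unrecorded limit carries its own risk. That is a reason to record the limit, not to leave the primary hypothesis on a different statistic.

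**Conclusion.** The concern holds. Sections 1.1.c and 2.0 set thresholds for between-method agreement that are not the validity rule in 8.1.b and 10.0, and the two kinds of criterion match only at a limit of 1.24 total SDs. A tighter limit lets 1.1.c succeed where the rule fails, and a looser one does the reverse. The algebra assumes equal SDs in the two methods and, apart from step 3, no bias. The direction and frequency of conflict in this study cannot be determined from the documents. The point should be fixed before the validity results are reported. It is an error in how success is worded and does not affect the design or data collection.

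**What to change.** - Reword 1.1.c and 2.0 so that limits of agreement on the paired difference, against the limit set under 8.1.b, are the single deciding criterion. State it separately for TUG (seconds) and 30s-CST (number of stands); 1.1.c now mentions only seconds.
- Record the limit for each test, the date it was set, and whether any Phase 2 paired data had been seen by then.
- Report the mean bias and both limits with 95% CIs.
- Keep ICC ≥ .80 as an explicitly secondary hypothesis and add it to section 10.0, in two-way, absolute-agreement, single-measure form with a 95% CI. Keeping it is better than deleting it, because it was stated in advance and Phase 2 had begun.
- Drop r ≥ .80 as a criterion.

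The cost is a sentence each in 1.1.c and 2.0, a line or two in 10.0 and a few lines of analysis, with no new data. The drawback is that .80 no longer decides success, and the intervals at 10 to 20 participants will be visibly wide.

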## PROTOCOL TITLE: Videoconferencing for Remote Assessment of Physical Performance

approval for future contact (see approved Future Contact form). Once 5 participants have successfully and safely completed the test protocol, we will proceed to Phase 4.

Phase 4: This phase is the same as Phase 3, except it includes newly enrolled participants, i.e., representing the first-time participants have enrolled/participated in this study. This will eliminate the practice effect that will occur in phase 3. This step will enroll 5-10 participants.

Therefore, the anticipated number of enrolled participants ranges from 30 to 52.

\*\* NOTE: Phase 1 and 2 above are already included in the currently approved study protocol (dated 25Oct2019). Phases 3 and 4 are new to the protocol. The four study phases are now introduced to better clarify the distinction between the approved study phases and the new study phases.

## 2.0 Background

Physical functioning, an important patient-reported outcome (PRO), is a key measure of physical health and well-being in older cancer survivors. Self-reported physical function is typically collected by questionnaire (e.g., SF-36, PROMIS, etc.). Objective measures of physical function (i.e., physical performance) are typically collected in a clinic setting (e.g., Short Physical Performance Battery, Rikli and Jones Senior Fitness Test, etc.). Currently, low-cost, valid, reliable, and easy to use methods to remotely assess physical performance in older adults do not exist. Wearable sensors are very expensive, proprietary, and/or require technicians present for testing.

Telerehabilitation studies have been conducted using videoconferencing to assess physical performance; however, to date, these studies have included a technician or study investigator in the same room as the study participant during the tests. Nor have these studies been tested in rural areas. We propose to evaluate the validity and reliability of using videoconferencing to assess physical performance tests self-administered by older cancer survivors. In order to evaluate validity, a member of the research team will need to be at the participant's home, and in the same room as the participant (face-to-face assessment of performance tests). However, the idea is to test if the participant is able to use the technology (an android tablet with videoconferencing software) to communicate with an off-site research investigator. We will also be testing the feasibility, acceptability, and most importantly the safety of having the participants perform two standard gerontologic physical performance tests in their own home (see below).

A friend, neighbor or relative is requested to be present during the assessment. This person will be able to communicate via the videoconferencing session with the investigator and must have access to a telephone should medical attention be required. However, if this person is unable to be present during the assessment once it has been scheduled, then the research investigator conducting the face-to-face assessment will cover their responsibilities. Face-to-face assessment is the traditional method for assessing these physical performance tests. We will be testing whether the remote assessment via videoconferencing can produce similar results (time in seconds to complete the tests) as the traditional (face-to-face) method.

The two different assessment methods (remote vs. face-to-face) should be within a reasonable margin of error ( $r \geq .80$ ) The two performance tests include the Timed Up & Go (TUG) Test and the 30-second chair stand test (30s-CST). The TUG test involves standing up from a standard

## PROTOCOL TITLE: Videoconferencing for Remote Assessment of Physical Performance

armchair, walking 10 feet, turning around (180° turn), and walking back to the chair and sitting down. This is a timed test, to be performed at the speed that is comfortable for the participant. The 30s-CST involves standing up from a chair and sitting down as quickly and safely as possible, preferably without the use of upper extremity support. It is measured by the number of times a person comes to a full standing position from a chair in 30 seconds. Both tests are timed with a stopwatch.

### 3.0 Inclusion and Exclusion Criteria

The proposed validation and reliability study will accrue between 30 and 52 adult cancer survivors from rural (~40%) and urban (~60%) areas who meet the following eligibility criteria:

The eligibility criteria will vary slightly depending on the recruitment method (New Mexico Tumor Registry [NMTR] vs. self-referrals). The NMTR criteria are based on increasing the likelihood of identifying and contacting cancer survivors who are still alive, healthy enough to participate in the study (vs. later stage disease), and for whom the contact information may still be accurate. Additionally, there is a 2 year lag in the completeness of data collected and managed by the registry. Several of these criteria are not necessary for recruiting through the general population, i.e., self-referrals who respond to study posted flyers. As this is a feasibility study, some of the eligibility criteria will be relaxed for self-referrals in order to assess our primary aims: the feasibility, acceptability, and safety of the study.

#### Screening for Recruitment via New Mexico Tumor Registry.

Initial screening will take place through the New Mexico Tumor Registry. *Only key research staff will be able to link the name of the cancer patient/survivor with the code number* (please refer to HRPO#: 85-001). Men and women who meet the following criteria will be identified:

- Diagnosed with one of the combinations of cancer-site and stage (SEER Summary Stage 2000) associated with a 60% or greater 5-year relative survival rate and common among older adults:

Cancer Site	Diagnosis Stage(s)	Percentage of cases by stage	5-year relative survival rate	Median age at diagnosis
Bladder	In situ, localized	51.0% 34.0%	95.8% 69.5%	73
	Localized	62.0%	98.8%	
Breast (female)	Regional	30.0%	85.5%	61
	Localized	39.0%	89.9%	
Colon & rectum (excluding carcinoid tumors & cancers of the appendix)	Regional	35.0%	71.3%	68
	Localized	67.0%	95.0%	
Corpus & uterus	Regional	21.0%	69.0%	62
	Localized	65.0%	92.5%	
Kidney & renal pelvis	Regional	17.0%	69.6%	64
	Localized	54.0%	77.4%	
Larynx	Localized			65

PROTOCOL TITLE: Videoconferencing for Remote Assessment of Physical Performance

Melanoma of the skin	Localized Regional	84.0% 9.0%	98.7% 64.7%	63
Non-Hodgkin Lymphoma	Localized Regional	25.0% 31.0%	82.6% 73.2%	66
Oral cavity & pharynx	Localized Regional	29.0% 47.0%	84.4% 66.0%	62
Ovary	Localized Regional	15.0% 21.0%	92.4% 75.2%	63
Prostate	Localized Regional	77.0% 13.0%	100% 100%	66

- Diagnosed within the past 2 to 5 years. Note: This time frame was selected to increase the probability of obtaining accurate/current contact information for the patients. Additionally, the two-year minimum increases the probability that the patient has completed primary cancer therapy.
- Cases with multiple primary cancers are ineligible (less likely to have completed treatment).
- Current age 60 or older at the time of study enrollment
- Known to be alive at the last ascertainment of vital status
- Current address within the following counties: Bernalillo, Sandoval, Santa Fe, Valencia, Torrance, Socorro, Cibola, Guadalupe, Chaves.

NOTE 1: Cases treated solely at Veterans Affairs will not be included in the selection of cases identified by the NMTR for the current study, per standing agreement between Veterans Affairs and the NMTR.

Note 2: Given the short study timeline, it is not feasible to seek tribal approval for contacting American Indian/Native American cancer patients who are included in the NMTR. Therefore, per standard NMTR policies and procedures when tribal IRB approval has not been obtained, American Indian and Native American cancer survivors will not be contacted by the NMTR on behalf of the study.

